2.0 OBJECTIVES

Primary

- To improve the accuracy of hypoxia imaging for head and neck cancers through pixel by pixel kinetic analysis of ^{18}F -FMISO tracer of dynamic PET images (Cohort 1 and Cohort 2).
- To detect on repeat ^{18}F -FMISO PET/CT scans whether there is a reduction of the ^{18}F -FMISO-avid or GIV_h 5 to 10 days into treatment with standard chemoradiotherapy for a series of locally advanced head and neck cancers (Cohort 1).
- To show that it is feasible to deliver 70Gy to primary site and 60Gy to the neck nodes in HPV+ patients who exhibit no evidence of hypoxia on their baseline ^{18}F -FMISO PET/CT scans or those who have early resolution of hypoxia on their early repeat ^{18}F -FMISO PET/CT scans (Cohort 1).
- To show that it is feasible to deliver 30Gy to the surgical bed and neck nodes in low-risk HPV+ patients who exhibit no evidence of hypoxia on their repeat ^{18}F -FMISO PET/CT (Cohort 2).
- To correlate the intensity of the ^{18}F -FMISO PET signal with the degree of immunohistochemical staining of hypoxia biomarkers for tissue obtained via biopsy (Cohort 1) and surgical resection (Cohort 2): HIF-1 α , Lysyl Oxidase, and Ki67 (an independent marker of tumor aggressiveness), among others.

Secondary

- To compare tumor heterogeneity derived from pixel-by-pixel kinetic analysis of PET scan and DWI-MRI (Cohort 1).
- To assess changes in tumor heterogeneity over the course of external beam RT using serial multiparametric MR and DCE-MRI scans (Cohort 1).
- To determine the potential of DCE-MRI data as a priori or early markers of tumor response to chemoradiation as well as long term disease-free survival after treatment (Cohort 1).
- To assess normal tissue response as a function of dose for parotid, submandibular glands, muscles and bones in the head and neck region during and after EBRT using serial multiparametric MR scans (Cohort 1).
- To bank specimens for further IRB/PB approved exploration of genetic analysis (Cohort 1 and Cohort 2).

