5 μ m formalin-fixed paraffin-embedded tissues will be deparaffinized in xylene, then rehydrated before antigen retrieval by microwaving in sodium citrate buffer (pH 6.0). The slides will then be incubated with a peroxidase block, followed by the primary antibody lysyl oxidase (LOX) according to the company's protocol. After hematoxylin counterstain, the slides will be cover slipped. Cytoplasmic staining will be considered as positive. The intensity and proportion of immunostaining will be scored on a semiquantitative six-point scale. Negative samples will receive a score of 0, whereas weak, moderate, and intense staining samples will receive a score of 1, 2, or 3, respectively. For the percentage tumor cell positivity the following scoring will be used: negative=0, 1–25%=1, 25–50%=2, >50%=3. Both the staining intensity and percentage positivity scores will be summed and tumors with scores ranging from 0 to 5 will be assigned to group 0=low lysyl oxidase, whereas those with a score of 6 will be assigned to group 1=high lysyl oxidase.

Ki-67

5 μ m formalin-fixed paraffin-embedded tissue will be subjected to IHC for Ki-67 staining using the MIB1 mouse mAb (Immunotech, Westbrook, ME) at a 1:500 dilution. Standard avidin-biotin-peroxidase complex techniques will be used. Antigen retrieval in heated citrate buffer at pH 6.0 will be applied. Slides will be counterstained with hematoxylin. Only nuclear staining of tumor cells will be considered positive. Ki67 expression will be determined by semi-quantitatively assessing the percentage of positive tumor cells.

Tissue Banking

With the patient's consent, we will bank the additional and left over tissue after the biopsy (Cohort 1) or surgical resection (Cohort 2) in Tissue Procurement Service (TPS). To further access this tissue, we will submit a plan to the Human Biospecimen Utilization Committee (HBUC). For retrospective feasibility studies, tissue use at MSKCC is governed by the HBUC. The HBUC has trans-departmental and multidisciplinary representation. As institutional policy, the HBUC will give special consideration to tissues requested for correlative analysis as part of a clinical trial, or to develop a tissue

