
The spatial extent of ^{18}F -FMISO PET imaging within the neck node(s) determines the underlying hypoxia tumor phenotype for both HPV positive and negative HNSCC. To determine whether baseline ^{18}F -FMISO PET/CT and/or early-response ^{18}F -FMISO PET/CT at 5-10 treatment days after chemotherapy and IMRT correlate with selected proliferative/hypoxia molecular markers, Wilcoxon rank sum tests will be used for each marker. Multiple testing adjustments such as Bonferroni procedures will be used. To investigate whether the extent of ^{18}F -FMISO PET/CT measured hypoxia at baseline and/or 5-10 treatment days into chemoradiation for both HPV positive and negative tumors correlates with the development of distant metastasis, Kaplan-Meier estimates will be calculated for each stratum and compared using the log-rank tests. When competing risks are present, Gray's test will be used to examine the correlation between the extent of ^{18}F -FMISO PET/CT measured hypoxia with the development of distant metastasis. To examine the potential correlations between the baseline and early

response ¹⁸F-FMISO PET imaging and tumor's underlying HPV status, we will apply Fisher's exact tests.

Multiparametric scans will also be obtained. We will attempt comparisons to ¹⁸F-FMISO PET results and immunohistochemistry hypoxia results, but due to the small pilot size of this exploratory aim, we may not produce significant results. In that case, we will present summary statistics and suggest directions for future study.

> For this study cohort, 14 eligible patients will be needed for the analysis. Assuming approximately 25% of the patients enrolled will not be eligible, we will plan to recruit 19 patients upfront. For evaluation on the efficacy of the regimen in this cohort, a simple decision rule will be implemented, which is as follows: If, among the total 14 eligible patients, we have at least 10 patients who are alive, followed and have a pathologic CR at 4 months from the end of the treatment, then we will declare the treatment modality using 30 Gy is feasible and worthy of further investigation. Any patient who died or is lost to follow up within 4 months from the end of radiotherapy will be regarded as a failure, i.e., without pathologic CR. Feasibility for the primary objective in cohort 2 will be defined according to aforementioned decision rule. This decision rule has the following probabilities of declaring success.

True Locoregional Control Rate									

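### The LOX rule separates only the top score from all others, though the primary objective is about degree of staining; the plan does not say which form is tested

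*Combined protocol and SAP*

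**What the plan says.** Section 4.1 (Lysyl Oxidase) scores each specimen on two parts. Negative samples get 0 for intensity, and "weak, moderate, and intense staining samples will receive a score of 1, 2, or 3, respectively". The percentage of positive tumor cells is coded "negative=0, 1–25%=1, 25–50%=2, >50%=3". The two parts are added, and the sum is then grouped: "tumors with scores ranging from 0 to 5 will be assigned to group 0=low lysyl oxidase", and "those with a score of 6 will be assigned to group 1=high lysyl oxidase".

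Section 2.0 names LOX in a primary objective, which is to correlate FMISO signal intensity "with the degree of immunohistochemical staining of hypoxia biomarkers for tissue obtained via biopsy" in Cohort 1, and likewise for resected tissue in Cohort 2.

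For the analysis, section 14.0 says that "Wilcoxon rank sum tests will be used for each marker" and that "Multiple testing adjustments such as Bonferroni procedures will be used". It does not say which variable forms the two groups of the rank sum test, or whether LOX enters as the score or as low/high. The other two named markers are not grouped in section 4.1: HIF-1α keeps a score from 0 to 12, and Ki-67 a percentage.

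**The concern.** The objective asks whether staining rises with uptake. The LOX rule answers a narrower question: whether tumors at the ceiling of the scale differ from all others. Any gradient between scores 0 and 5 becomes invisible, and no reason is given for treating LOX differently from the other two markers.

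Tissue is scarce. Section 1.0 gives 19 surgical patients. Section 3.0 (Immunohistochemistry) reports nearly 20 biopsy specimens so far, close to half of them without tumor cells. With so few specimens and a multiplicity adjustment, LOX could look unrelated to FMISO because recorded information was set aside before testing.

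**Working it through.** The plan gives no sample size, effect size, power or expected share of top scores for LOX, so there is no figure of its own to reproduce.

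**Step 1: attainable scores.** A positive specimen scores 1 to 3 on each part, so its sum runs from 1+1 = 2 to 3+3 = 6. A negative specimen scores 0. The attainable values are 0, 2, 3, 4, 5, 6, and the cut merges five of the six. High requires 3+3, that is, intense staining in more than 50% of cells. Moderate staining in more than 50% of cells gives 2+3 = 5, and intense staining in 25–50% gives 3+2 = 5. Both are classed with 0.

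**Step 2: information kept by a two-group cut.** Under a bivariate normal model, let p be the share in the high group. Efficiency relative to a continuous marker is φ(z_p)² / [p(1−p)], where φ is the normal density at the cut point.

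- p = 0.10: 0.1755² / 0.09 = 0.34
- p = 0.20: 0.2800² / 0.16 = 0.49
- p = 0.30: 0.3477² / 0.21 = 0.58
- p = 0.50: 0.3989² / 0.25 = 0.64
- p = 0.70: 0.3477² / 0.21 = 0.58

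**Step 3: power by simulation.** All inputs are assumptions except where a source is given:

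- n = 29: the 19 surgical patients plus about 10 biopsies with tumor (about half of nearly 20), one independent value each.
- Latent correlation 0.5.
- Two-sided alpha 0.05/3 = 0.0167, for the three named markers (the plan does not state the number of tests).
- Scores below 6 equally frequent.

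The full score is tested by Spearman correlation with continuous FMISO. The cut is tested by a rank sum comparison of FMISO between score 6 and scores 0–5. Relative loss is (full − cut)/full.

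| Share scoring 6 | Full score | 6 v 0–5 | Relative loss |
|---|---|---|---|
| 10% | 0.57 | 0.13 | 0.44/0.57 = 77% |
| 20% | 0.58 | 0.27 | 0.31/0.58 = 53% |
| 30% | 0.54 | 0.30 | 0.24/0.54 = 44% |
| 50% | 0.49 | 0.36 | 0.13/0.49 = 27% |
| 70% | 0.39 | 0.32 | 0.07/0.39 = 18% |

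A second run with 4,000 simulations per setting agreed to within about 3 points, so small differences should not be read closely.

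**Step 4: other sample sizes, same correlation and alpha.** At n = 19, full score against cut is 0.35 v 0.09 at a 10% share and 0.20 v 0.17 at 70%. At n = 60 it is 0.93 v 0.42 and 0.77 v 0.74.

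**Step 5: the other reading of section 14.0.** Suppose FMISO supplies the two groups, split at its median (an assumption), and the full LOX score enters the rank sum test. At n = 29, power is about 0.36, 0.35, 0.34, 0.29 and 0.21 for shares of 10%, 20%, 30%, 50% and 70%. That beats the LOX cut at 10–20%, is about level with it at 30% and is worse at 50–70%. It is below the full-score correlation throughout.

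**The case against.** The strongest reply is that section 14.0 never says the two LOX groups are what is tested. HIF-1α and Ki-67 have no groups, so a rank sum test on them needs FMISO to define the groups, and the graded LOX score could enter the same way. This stands: the loss is conditional, and the certain defect is an unjustified cut together with an unstated analysis form. It does not settle the matter, because section 4.1 presents the two groups as the end point of LOX scoring, and splitting FMISO has a cost of its own (step 5).

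A reader might infer that the cut leaves a small high group and so destroys most of the power. The documents do not support that. They give no share scoring 6, and a top score need not be rare: section 3.0 cites HIF-1α overexpression in 94% of one oropharyngeal series and describes LOX as regulated by HIF-1α. That does not establish the share either, but it rules out assuming that it is small. In the table, more than half of the power is lost at shares of 10% and 20%, not at 30% to 70%.

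It is also fair to say that the sample size and the correlation are assumptions, that LOX is one of three named markers, that no treatment decision depends on it, and that the component scores allow an ordinal analysis later.

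**Conclusion.** The point holds as a free improvement of minor weight. The rule discards the ordering among scores 0 to 5 without a stated reason, for a marker in a primary objective about degree of staining, and section 14.0 leaves open which form is tested. If the two groups are used, the loss at about 29 specimens runs from small (0.39 to 0.32 when 70% score 6) to severe (0.57 to 0.13 when 10% do). The full score had the higher power in every setting tried. The direction does not depend on the unknown share, but the size does, and it also rests on the assumed correlation, alpha, number of independent specimens and spread of the lower scores.

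**What to change.** In section 14.0, name the summed LOX score, treated as an ordinal variable, as the main form for the FMISO correlation, for example by Spearman correlation with FMISO intensity kept continuous. Keep 6 versus 0–5 as a secondary analysis with a reason for the cut, and report how many specimens reach 6. State the unit of analysis (one value per patient, or a method that allows for several specimens from one patient). Amend section 4.1 so that the grouping is no longer the only stated result of LOX scoring.

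The cost is wording alone. Both component scores are already part of the planned reading, so no further tissue, patients or procedures are needed. The change should be made before the marker results are compared with the imaging.

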4.2 Intervention

For patients in Cohort 1, there will be no change or intervention in a patient's treatment regime using chemoradiation where both the primary and the neck nodes receive 70Gy if the tumors are not associated with HPV or if there is no resolution of hypoxia on their repeat ¹⁸F-FMISO PET/CT scan. This is currently one accepted standard of care.

Patients in Cohort 1 with tumors that are positive for HPV who exhibited no evidence of hypoxia on their baseline ¹⁸F-FMISO PET/CT scan or whose tumors have early resolution of hypoxia on their repeat early response ¹⁸F-FMISO PET/CT scan will undergo an alternative treatment where the primary tumor site receives 70Gy while the neck nodes receive 60Gy followed by a planned FDG PET/CT scan and observation.

Select Cohort 2 HPV+ tumors that demonstrate no evidence of hypoxia on an ¹⁸F-FMISO PET scan will receive 30Gy to the surgical bed and neck lymph nodes concurrent with standard chemotherapy followed by a 3 to 4-month post-treatment neck dissection. In patients who exhibit a complete response with this method of treatment, no further treatment is necessary. For patients within this select group who still have pathologic

nodal disease, further standard chemoradiation will be given. All other patients in this cohort (i.e. those who are not in the select HPV+ tumor group outlined above) will receive standard of care treatment following their surgery.

5.0 THERAPEUTIC/DIAGNOSTIC AGENTS

DCE-MRI studies will be acquired using a fast multi-phase spoiled gradient echo sequence. A Gadolinium-based agent will be used for DCE-MRI studies. This is the standard contrast agent used with MRIs.

¹⁸F-FMISO is prepared and tested for quality assurance in this study at MSKCC or by an equivalent qualified supplier. The radiopharmaceutical is being utilized in this protocol under a MSKCC IND.

Radionuclide dosimetry

Biodistribution data on ¹⁸F-FMISO has been obtained for 60 patients at the University of Washington, School of Medicine, and dosimetry was performed. The normal organ doses absorbed following ¹⁸F-FMISO administration was published by Graham et al (15) and is summarized in the table below.

Radiation Absorbed Doses to Organs following ¹⁸F-FMISO administration.

Target Organ	Median Dose (mGy/MBq)	Dose (cGy) per 10mCi (370 MBq) injection	Total Procedure Dose (cGy) Tracer + 3 attenuation CT scans
Adrenals	0.0166	0.61	3.31
Brain	0.0086	0.32	3.02
Breasts	0.0123	0.46	3.16
Gall bladder wall	0.0148	0.55	3.25
Lower Large Intestine	0.0143	0.53	3.23
Small Intestine	0.0132	0.49	3.19
Stomach	0.0126	0.47	3.17
Upper Large Intestine	0.0140	0.52	3.22
Heart Wall	0.0185	0.68	3.38
Kidney	0.0157	0.58	3.28
Liver	0.0183	0.68	3.38
Lungs	0.0099	0.37	3.07
Muscle	0.0142	0.53	3.23
Ovaries	0.0176	0.65	3.35
Pancreas	0.0179	0.66	3.36
Red Marrow	0.0109	0.40	3.10
Bone Surface	0.0077	0.28	2.98
Skin	0.0048	0.18	2.88
Spleen	0.0163	0.60	3.30
Testes	0.0146	0.54	3.24
Thymus	0.0155	0.57	3.27
Thyroid	0.0151	0.56	3.26
Urinary Bladder Wall	0.0210	0.78	3.48
Uterus	0.0183	0.68	3.38
Eye Lens	0.0154	0.57	3.27

Total Body	0.0126	0.47	3.17
------------	--------	------	------

The original approved protocol MSKCC 04-070 consisted of 3 injections of 370 MBq of ¹⁸F-FMISO per patient. The current protocol involves up to 2 injections of 370 MBq of ¹⁸F-FMISO per patient. The dose estimates derived from the University of Washington data were used to provide the dose from the single 10 mCi administration of ¹⁸F-FMISO and were confirmed by our pilot study. The urinary bladder wall is subject to the largest dose of 0.78 cGy. This is an insignificant addition to the total therapeutic radiation dose that the patient will receive for his or her head and neck cancer. In addition, the patient will receive a low dose CT attenuation scan each contributing an addition of 0.9 cGy whole body dose to the patient. The dose to the eyes from the combination of an ¹⁸F-FMISO and CT scan would be $0.57 + (3 \times 0.9)$ cGy = 3.27 cGy. This will also not significantly add to the total radiation dose that the patient will receive from treatment for his or her head and neck cancer.

Also note that these radiation doses are overestimates, because the CT scan (and therefore dose) will only apply to a single 15cm field of view surrounding the lesion of interest. For example, for patients in which the lesion is remote from the eye, the lens will only receive a dose of 0.57 cGy resulting from the ¹⁸F-FMISO administration and nothing from the CT.

6.0 CRITERIA FOR SUBJECT ELIGIBILITY

6.1 Subject Inclusion Criteria for Cohort 1 and Cohort 2

- Histologically confirmed diagnosis of head and neck carcinoma (excluding nasopharynx, paranasal sinus, salivary, and thyroid malignancies). Any unknown primary squamous cell carcinoma of head and neck with gross nodes is allowed (2002 AJCC)
- 18 years of age or older
- Must not have received prior radiation therapy or chemotherapy for this diagnosis.
- Patients who have had their primary site tumor removed by surgery but still present with grossly enlarged lymph nodes are eligible for this study.
- Karnofsky performance status ≥ 70 .

6.2 Subject Exclusion Criteria for Cohort 1 and Cohort 2

- All nasopharyngeal, paranasal sinus, salivary cancer, and thyroid malignancies
- Prior chemotherapy or radiotherapy within the last three years
- Patients that underwent previous surgical resection for the same disease (except for biopsy or surgery removing primary site tumor but still present with grossly enlarged lymph nodes)
- Any prior radiotherapy to the head and neck region

- Pregnant (confirmed by serum b-HCG in women of reproductive age) or breast feeding

6.3 Subject Exclusion Criteria for Optional Contrast MRIs – Cohort 1 Only

- Subjects with a known contraindication to the standard MRI contrast agent (Gadavist, a gadolinium-based contrast agent) and/or a recent estimated glomerular filtration rate (eGFR) of 30 or less will be excluded from all DCE-MRIs, and will instead receive non-contrast MRIs at the DCE-MRI time points.

7.0 RECRUITMENT PLAN (WITH LIMITED WAIVER OF AUTHORIZATION)

Patients will be evaluated by an attending physician from the Department of Radiation Oncology and entered onto the study and into the appropriate cohort if they are appropriate candidates. The attending physician will obtain informed consent from the eligible patient.

Potential research subjects will be identified by a member of the patient's treatment team, the protocol investigator, or research team at MSKCC. If the investigator is a member of the treatment team, s/he will screen their patient's medical records for suitable research study participants and discuss the study and their potential for enrolling in the research study. Potential subjects contacted by their treating physician will be referred to the investigator/research staff of the study.

The Principal Investigator may also screen the medical records of patients with whom they do not have a treatment relationship for the limited purpose of identifying patients who would be eligible to enroll in the study and to record appropriate contact information in order to approach these patients regarding the possibility of enrolling in the study.

During the initial conversation between the investigator/research staff and the patient, the patient may be asked to provide certain health information that is necessary to the recruitment and enrollment process. The investigator/research staff may also review portions of their medical records at MSKCC in order to further assess eligibility. They will use the information provided by the patient and/or medical record to confirm that the patient is eligible and to contact the patient regarding study enrollment. If the patient turns out to be ineligible for the research study, the research staff will destroy all information collected on the patient during the initial conversation and medical records review, except for any information that must be maintained for screening log purposes.

In most cases, the initial contact with the prospective subject will be conducted either by the treatment team, investigator or the research staff working in consultation with the treatment team. The recruitment process outlined presents no more than minimal risk to the privacy of the patients who are screened and minimal PHI will be maintained as part of a screening log. For these reasons, we seek a (partial) limited waiver of authorization for the purposes of (1) reviewing medical records to identify potential research subjects and obtain information relevant to the enrollment process; (2) conversing with patients

regarding possible enrollment; (3) handling of PHI contained within those records and provided by the potential subjects; and (4) maintaining information in a screening log of patients approached (if applicable).

8.0 PRETREATMENT EVALUATION

All patients will receive the necessary scans and tests according to the standard of care for their head and neck cancer.

9.0 TREATMENT/INTERVENTION PLAN

For patients in Cohort 1, there will be no change or intervention in a patient's treatment regime using chemoradiation where both the primary and the neck nodes receive 70Gy if the tumors are not associated with HPV or if there is no resolution of hypoxia on their repeat ¹⁸F-FMISO PET/CT scan.

Patients in Cohort 1 with tumors that are positive for HPV who exhibited no evidence of hypoxia on their baseline ¹⁸F-FMISO PET/CT scan or whose tumors have early resolution of hypoxia on their repeat early response ¹⁸F-FMISO PET/CT scan will undergo an alternative treatment where the primary tumor site receives 70Gy while the neck nodes receive 60Gy followed by a planned FDG PET/CT scan and observation.

Select Cohort 2 HPV+ tumors that demonstrate no evidence of hypoxia on an ¹⁸F-FMISO PET scan will receive 30Gy to the surgical bed and neck lymph nodes concurrent with standard chemotherapy followed by a 3 to 4 month post-treatment neck dissection. In patients who exhibit a complete response with this method of treatment, no further treatment is necessary. For patients within this select group who still have pathologic nodal disease, further standard chemoradiation will be given. All other patients in this cohort (i.e. those who are not in the select HPV+ tumor group outlined above) will receive standard of care treatment following their surgery.

Please note that for patients who receive a repeat ¹⁸F-FMISO PET/CT scan, the repeat ¹⁸F-FMISO PET/CT scan will only be performed 5-10 days into chemoradiotherapy treatment. For Cohort 1 patients, a repeat ¹⁸F-FMISO PET/CT scan will only be performed if the pretreatment baseline ¹⁸F-FMISO PET scan is positive for hypoxia.

Chemotherapy will be administered in two doses. Chemotherapy will begin +/- 3 days from the first day of radiation therapy. The second cycle of chemotherapy will begin 3 weeks later (+/- 5 days), although delays for safety (e.g, low white blood count, elevated creatinine) are allowed. Standard chemotherapy with either Cisplatin or Carboplatin/5-Fluorouracil is strongly recommended. Any other schedule (e.g, weekly chemotherapy) is discouraged and requires approval of the principal investigator.

- Patients should receive standard high dose Cisplatin chemotherapy at 100 mg/m². If the patient is unfit or cannot tolerate Cisplatin, the treating physician must discuss with study medical oncologist, [name], to jointly confirm what chemotherapy should be given in place of Cisplatin.

- If a patient is not tolerating Cisplatin well, dose modification(s) must be discussed with study investigator, [name], prior to making any changes.

Patients on main campus, unless contraindicated, will have a recommended MRI at pre-treatment (Cohort 1), recommended MRIs approximately weekly (Cohort 1), and a recommended MRI post-treatment at 3 months, 6 months, and 1-year post-treatment (+/-4 weeks) when possible (Cohort 1). Cohort 2 patients will not receive approximately weekly MRIs, and will not receive a post-treatment MRI at 3 months, 6 months, and 1 year post-treatment.

Central review of all radiation treatment plans must be reviewed by study PI [name] and/or investigator [name] prior to initiating radiation treatment.

